## 2. Study Objectives

### 2.1 Study 1

Study 1 will test the central hypothesis that high dose isoflurane anesthesia inducing EEG burst suppression (High ISO/BS+) is a more effective intervention for severe depression when compared to a low dose isoflurane anesthesia that does not induce EEG burst suppression (Low ISO/BS-). The proposed study is a randomized, double-blind trial that will evaluate 30 actively depressed participants with moderate to severe depression. Depression outcomes will be compared between two groups of participants (n=15 per group) who have received 10 treatment applications over a period of three weeks of either High ISO/BS+ or Low ISO/BS-.

Aim 1. To determine whether High ISO/BS+ is more effective than Low ISO/BS- in producing either a treatment response (defined as 50% reduction in depression scores) or full remission of depressive symptoms. We hypothesize that significantly more depressed participants randomized to receive 10 treatments of High ISO/BS+ compared to Low ISO/BS- will show a positive treatment response or full remission by treatment end. Based on the STAR\*D Trial, a responder is a participant showing 50% reduction in depression score and full remission is defined as a score of 0-10 on the HRSD-24 scale and score of 0-5 on the QIDS-SR16.

Aim 2. Preliminary data on neural and immune pathways that are differentially affected by the 2 treatments and associated with antidepressant effects will be explored by comparing changes from pre-treatment to post-treatment in full transcriptome leukocyte gene expression (using the RNA Seq method).

Aim 3. To measure the central neurochemical effects of isoflurane treatment, we will quantify neurotransmitter levels (GABA and glutamate) using magnetic resonance spectroscopy.

### 2.2 Pilot Study 2

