Initial trials examining the antidepressant efficacy of High ISO were promising. Langer et al conducted two preliminary studies that demonstrated comparable efficacy between 6 sessions of High ISO vs. ECT, with High ISO having the advantage of not causing memory loss. Antidepressant efficacy was also supported by Engelhardt et al who used High ISO treatments followed by ECT and by Carl et al who again found comparable antidepressant efficacy with the 2 treatments. These positive findings were followed by two negative trials. Greenberg et al treated 6 elderly individuals with High ISO, with little improvement. Garcia-Toro et al examined the efficacy of 4 low dose treatments of a related anesthetic, sevoflurane, in another pilot trial, and saw a 24% reduction in depressive symptoms. Since sevoflurane is less effective in inducing BS+ than isoflurane, the dose could have been too low to achieve consistent BS+. Moreover, 4 treatments are fewer than are recommended for ECT (8-12 sessions) and thus it is not surprising that the effect size was small. Unfortunately, further investigations of High ISO as an antidepressant halted for quite some time.

Because of its early success and the design limitations associated with the negative trials, our group conducted a small open-label study to renew investigation of the potential antidepressant efficacy of High ISO. In the study, 8 patients with treatment resistant depression were treated with 10 sessions of high dose ISO with confirmed EEG burst suppression (High ISO/BS+). The comparison group was 20 patients treated with bifrontal ECT. High ISO/BS+ led to an antidepressant response (defined as a 50% reduction in HRSD score) in 75% of participants and a rate of full remission of depressive symptoms identical to ECT (50%). Furthermore, the response rates for the High ISO/BS+ and ECT treatments were comparable, as measured by QIDS self-report. In addition, improvement was maintained for 4 weeks after treatment for most participants in the High ISO/BS+ group. Furthermore, participants treated with High ISO/BS+ showed significantly less neurocognitive impairment following their treatments than was shown by ECT-treated patients.

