#### **4.5 Study Visits**

**Screening:** Patients who have been referred or have volunteered for the study will be screened in person or by phone to verify that inclusion and exclusion criteria have been met.

**Consent procedures:** Each patient will be given a full verbal explanation of the study procedures, including risks, benefits, and alternatives, and will be given a copy of the approved written consent form. The patients will be given the opportunity to review the consent form and to discuss any questions or concerns with their own psychiatrist, our study investigators, or others if necessary prior to beginning study treatment procedures.

**Baseline:** Prior to the first treatment, depression severity will be assessed via a psychiatric interview, including completion of the HRSD-24 and MoCA, which will also verify inclusion and exclusion criteria. Immediately before treatment 1, the participant will complete the QIDS and a blood sample will be obtained from the IV line.

**Randomization (Study 1 only):** Participants who meet study criteria will be randomly assigned in blocks of 4 to either high or low dose isoflurane (High ISO/BS+ vs. Low ISO/BS-). We anticipate up to 15 participants in each arm; this sample size was defined by our prior study in which 8 participants were adequate to show significant antidepressant effects.

**Leukocyte Gene Expression:** Although our study is designed with EEG burst suppression as our primary target mechanism, we acknowledge that its effects must be mediated via specific neural pathways. Thus, we will explore possible neural and immune pathways associated with the antidepressant effects of deep anesthesia. Changes in full transcriptome leukocyte gene expression from pre- to post-treatment will be assessed from blood samples drawn before the first treatment and within 48 hours of the final (10th) treatment. In particular, we will examine the possible role of GABA-ergic and ATP-responsive ion channel pathways as well as other putative depression- or suicidality-linked neuroimmune pathways. We will also evaluate other ATP-responsive ion channels (purinergic, acid sensing and transient vanilloid receptor) or other

genes including IL-10 and other cytokines, SAT1, PTEN, MARCKS and MAP3K3 previously associated with refractory depression or suicidality by our group and others. [42918](#)

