## **7. Statistical Considerations**

Statistical analyses will employ a statistical mediation model framework. Any participant missing necessary information will be excluded from statistical analysis. Only participants with usable data will be included in the analyses. If the original statistical plan becomes infeasible, the original plan and the modifications made will be reported.

**7.1 Aim 1.** To determine if significantly more depressed participants randomized to receive 10 treatments of High ISO/BS+ will show a positive treatment response (defined as 50% reduction in depression scores) or achieve full remission of symptoms by treatment end compared to those in the Low ISO/BS-group, odds of treatment response and remission will be compared between groups using logistic regression analysis with positive response at treatment end (yes/no) as the dependent variable, and treatment group (High ISO/BS+ vs Low ISO/BS-) as the independent variable. Positive treatment response is defined as 50% reduction in depression scores, and remission will be defined as a score of 0-10 on the HRSD-24 scale.

Covariates will include baseline depression severity and possibly other baseline demographic and clinical measures as needed.

**7.2 Aims 2 and 5.** Using RNA SEQ methods, we will also explore whether participants who respond to treatment show blood-based changes in gene expression of neural and immune pathways previously associated with refractory depression or suicidality by our group or others. A t-test or non-parametric Wilcoxon test will be used, as appropriate. Change from baseline to end of treatment in gene expression levels will be correlated with change from baseline to end of treatment in HRSD-24.

**7.3 Aim 4.** In the open-label trial of propofol, initial evidence of efficacy will be defined by the percent of participants who show at least a 20% reduction in both HRSD and QIDS scores (initial improvement, as employed in the STAR D investigation) and who are propofol/BS+ responders (defined as 50% or more reduction in both HRSD-24 and QIDS scores). Secondary evidence of efficacy will be defined by comparing the percent of participants who are responders to propofol/BS+ vs. to the Low ISO/BS- control condition in the randomized trial.

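### Section 7.1 fits logistic regression in at most 15 per arm with no small-sample method, no named test and an open covariate list, so the odds ratio may have no finite estimate and tends to be overstated if several covariates are added

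*Combined protocol and SAP*

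**What the plan says.** Study 1 randomises 1:1. Section 2.1 says: "Depression outcomes will be compared between two groups of participants (n=15 per group"). Section 4.5 gives no formula for that size; it says "this sample size was defined by our prior study in which 8 participants were adequate to show significant antidepressant effects".

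For Aim 1, section 7.1 says "odds of treatment response and remission will be compared between groups using logistic regression analysis with positive response at treatment end (yes/no"), with treatment group as the independent variable. On adjustment it says: "Covariates will include baseline depression severity and possibly other baseline demographic and clinical measures as needed". There is no list, no upper limit and no selection rule.

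The opening of section 7 excludes participants who lack necessary data, so the analysed number can fall below 30. Its only provision for a model that cannot be fitted is: "If the original statistical plan becomes infeasible, the original plan and the modifications made will be reported". No alternative method is named, and section 7 states no alpha level and no choice between Wald and likelihood-ratio tests.

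Section 5.3.1 makes change in HRSD-24 the primary outcome measure, but section 7 contains no between-arm test of that change. The logistic model in 7.1 is therefore the only stated efficacy comparison between the Study 1 arms.

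**The concern.** Maximum-likelihood logistic regression has no finite odds ratio when one arm has all or no events, or when a combination of covariates separates responders from non-responders perfectly. Both are realistic in a sample this small, and each added covariate makes the second more likely. When a finite estimate does exist, maximum likelihood with many terms per event tends to push it away from 1.

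Remission is analysed as well as response. It is the rarer event, and participants have already failed at least two antidepressant treatments, so few or no remissions on Low ISO is plausible.

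Three things are at stake: whether the Aim 1 odds ratio can be reported, whether its size can be believed, and whether its p-value is fixed by the plan or depends on choices still open at analysis.

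**Working it through.** **Inputs from the plan.** 15 per arm (section 2.1). Prior High ISO response rate 75%: "High ISO/BS+ led to an antidepressant response (defined as a 50% reduction in HRSD score) in 75% of participants" (section 3). Prior remission rate 50% (section 3). Both come from 8 patients.

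**Assumptions.** The Low ISO rate is not given, and section 4.3 says the effect of the low dose is unknown, so a range is used. Alpha is taken as 0.05 two-sided.

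**The plan's own figure.** 15 per arm cannot be reproduced, because no control rate, alpha or power is stated. With 80% power and the usual uncorrected two-proportion formula, 15 per arm results for 75% v about 25%, or for 50% v about 5%. The second pairing is one in which an empty cell is likely.

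**Step 1: empty control arm.** P(no events in 15) = (1 − p)^15.
- p = 5%: 0.95^15 = 0.463
- p = 10%: 0.90^15 = 0.206
- p = 20%: 0.80^15 = 0.035

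For 75% v 20%, adding the chance that all 15 on High ISO respond (0.75^15 = 0.013) brings the total to about 5%.

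**Step 2: what the tests give.** Take 7/15 v 0/15 with no covariates.
- Likelihood ratio: G² = 2 × {[7 ln(7/15) + 8 ln(8/15)] − [7 ln(7/30) + 23 ln(23/30)]} = 2 × (−10.36 + 16.30) = 11.87 on 1 df, p = 0.0006.
- Fisher: 2 × C(15,7)/C(30,7) = 2 × 6435/2035800, p = 0.006.
- Wald: the standard error diverges (about 12,444 where the fit stops), p about 1.

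The same data and model give p near 1 or below 0.001, depending on a choice the plan does not make.

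**Step 3: effect of added covariates.** Simulated trials of 15 per arm, with a baseline log odds ratio of 0.5 per SD and three binary covariates of no true effect. At 50% v 10% the expected events are 7.5 + 1.5 = 9, spread over five model terms. The range of failed fits runs from a covariate prevalence of 50% (lower end) to 30% (upper end).

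| High v Low | True OR | No finite fit | Median OR when finite |
|---|---|---|---|
| 50% v 10% | 9 | 24-33% | 13-14 |
| 50% v 20% | 4 | 7-13% | 5.2-5.5 |

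Rarer covariates are worse: at 20% prevalence, failure reaches about 49% and 34%. Mixed continuous and binary covariates are milder: at 50% v 20%, failure is 5% with three covariates in total and 10% with five.

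**Step 4: baseline severity alone.** At a 20% control rate, failure is 2-4%. Median odds ratios are 4.5 v true 4 (50% v 20%), 8.2 v 7 (75% v 30%), 15.3 v 12 (75% v 20%) and 9.2 v 9 (50% v 10%). At 50% v 10%, failure can still reach about 24%, mostly from the empty cell in step 1.

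**Step 5: false positives.** Null trials with a 40% event rate and baseline always in the model, taking the smallest treatment p over all subsets of the optional covariates:

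| Test | Fixed model | Best of 3 optional | Best of 5 optional |
|---|---|---|---|
| Likelihood ratio | 6.2-6.8% | 12.9% | 18.6% |
| Wald | 3.6-4.4% | 7.8% | 8.8% |

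The five-covariate runs number 500, so the Monte Carlo standard error at 18.6% is √(0.186 × 0.814/500) = 1.7 points.

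Without any selection, the likelihood-ratio test with five fixed covariates rejects 9.7% (both arms 30%) or 13.9% (both arms 20%).

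**Step 6: the alternative.** Firth estimates were always finite. Their mean log odds ratio was within about 2% of truth with baseline alone and 7% with three more covariates. Type I error of the profile test was about 5%.

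**The case against.** The strongest reply is that the plan commits only to arm and baseline severity. Further covariates are a possibility, and for that minimal model step 4 shows little harm once the control rate is 20% or more. Response, the named dependent variable, had a prior rate of 75%, and the control rate could be well above 20%. This stands, and it limits the size of the problem.

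A reader might infer that the test fails exactly when the treatment works best. The documents do not support that, because they do not name the Wald test. The likelihood-ratio test on 7/15 v 0/15 rejects clearly. What is lost is the odds ratio and any certainty about which p-value counts. Nor do the two problems fall on one test at their largest: Wald loses power under separation, while the likelihood-ratio test carries the larger false-positive rates.

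A reader might also infer that covariates will be picked after the results are known. Section 7.1 is silent on timing. Its wording permits this but does not state it, and the undertaking to report modifications is a real, if weak, commitment to transparency.

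Finally, Firth is not the only sound choice. Exact logistic regression or a pre-stated Fisher test would also avoid the failure. That is fair; the need is to fix one method in advance.

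**Conclusion.** The concern holds in a limited form. As written, the Aim 1 model may give no finite odds ratio if Low ISO events are few or several covariates are added, and with several covariates it tends to overstate the odds ratio. It does not always overstate: there is no bias when the arms do not differ, and almost none at 50% v 10% with baseline alone.

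The sizes rest on an assumed control rate, on the number and prevalence of covariates, and on prior rates from 8 patients. Exclusions for missing data would worsen them: at 12 per arm with five covariates, the fit fails in 33% of trials at 75% v 20% and 48% at 50% v 10%.

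The false-positive figures in step 5 apply only if covariates are chosen for the most favourable result. They show what the wording allows, not what the investigators intend. This should be fixed before unblinding, but it does not make the planned analysis unusable.

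**What to change.** In section 7.1:
- Specify Firth penalised-likelihood logistic regression, separately for response and for remission, with arm and baseline HRSD-24 as the only terms.
- State that the test and confidence interval come from the profile penalised likelihood, and state the alpha level.
- Report the High minus Low risk difference with an exact or score interval, and Fisher's or Boschloo's test as a check.
- Delete the clause that allows further baseline measures, and label any other adjusted model a sensitivity analysis.

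The cost is wording only. The downsides are slight shrinkage of the odds ratio and no adjustment in the main model for prognostic factors other than baseline severity.

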## **5.3 Clinical Assessments**

**5.3.1 Primary Response Assessments:** The primary outcome measure is change in depressive symptoms assessed by the Hamilton Rating Scale for Depression (HRSD-24), which is the most widely used method of evaluating the effectiveness of treatments to relieve depression. HRSD-24 will be administered as part of a clinical interview by blinded investigators prior to beginning the treatments, then repeated before treatment #6 and at the end of treatments.

**5.3.2 Secondary Response Assessments to be acquired before each treatment:** Also as standard of care for patients receiving ECT, the participant will fill out the Quick Inventory of Depressive Symptomatology (QIDS-SR) which is a patient self-report measure of depressive symptoms prior to each treatment session. QIDS scores will also be used as a safety measure. If 2 consecutive QIDS scores indicate worsening of depressive symptoms, below pre-treatment values, the study participant will meet with one of the study Psychiatrists to discuss treatment alternatives. The Montreal Cognitive Assessment (MoCA), Generalized Anxiety Disorder scale (GAD-7), and Work and Social Adjustment Scale (WSAS) will be administered prior to beginning the treatments, then repeated before treatment #6, and 48-72 hours post treatment #10.

**5.3.3 Follow-up Assessments to be acquired monthly for up to 6-months post treatment period:** Follow-up assessments will include QIDS-SR, WSAS, and an opened ended question about the participant's experience during the study. Follow-up assessments will be administered over the phone or by email with a link to an electronic survey housed on REDCap (a secure online database). A voicemail may be left (with prior permission) regarding the follow-up assessments.

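### Section 7.1 compares the randomised arms only on binary outcomes at treatment end; the serial QIDS-SR and the mid-course HRSD-24 have no planned High versus Low analysis

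*Combined protocol and SAP*

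**What the plan says.** Section 7.1 (Aim 1) compares the odds of response and of remission between the arms "using logistic regression analysis with positive response at treatment end (yes/no) as the dependent variable", adjusting for baseline severity and possibly other baseline measures. Response is a halving of depression scores, with no scale named. Remission is an HRSD-24 score of 0-10.

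More is collected than these analyses use:

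- **HRSD-24** (Section 5.3.1). Change on this scale is the primary outcome measure. It is taken before treatment starts, "then repeated before treatment #6 and at the end of treatments".
- **QIDS-SR** (Section 5.3.2). This is the secondary response assessment; participants "fill out the Quick Inventory of Depressive Symptomatology (QIDS-SR) which is a patient self-report measure of depressive symptoms prior to each treatment session". Under Section 4.5 the score before treatment 1 is the pre-treatment value, so nine scores are on treatment. The Schedule of Activities shows no QIDS at the Post Tx visit.

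Section 2.1 gives the size: "Depression outcomes will be compared between two groups of participants (n=15 per group". Section 4.5 gives the reason: "this sample size was defined by our prior study in which 8 participants were adequate to show significant antidepressant effects". Section 7 excludes any participant with missing information. It also announces a mediation framework, but names no outcome, time points or model for it.

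**The concern.** No analysis in Section 7 compares High with Low on the course of QIDS-SR or uses the HRSD-24 taken before treatment 6. Change in HRSD-24, the stated primary measure, has no between-arm analysis as a continuous quantity.

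With 15 per arm, reducing a graded score to yes/no is expensive. The exclusion rule adds to this: a participant who stops after treatment 7 may contribute nothing to efficacy despite seven recorded QIDS-SR scores. Early exits are foreseeable, because Section 6.3 provides both for withdrawal and for offers of other treatment during the course. Without a named model, any later analysis of the series would also be a choice made after seeing the data.

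**Working it through.** **Inputs.** From the documents: 15 per arm, and a prior open-label group of 8 with "antidepressant response (defined as a 50% reduction in HRSD score) in 75% of participants". The documents give no alpha, power, Low-arm response rate, SD or correlation, so there is no power figure to reproduce. Assumed throughout: two-sided 5%, and complete data except in step 5.

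**Step 1. Cost of dichotomising, closed form.** Take 75% versus an assumed 40% response.

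- Binary: the mean proportion is 0.575. SE under the null = √(0.575 × 0.425 × 2/15) = 0.1805. SE under the alternative = √[(0.75 × 0.25 + 0.40 × 0.60)/15] = 0.1688. Power = Φ[(0.35 − 1.96 × 0.1805)/0.1688] = Φ(−0.02) = 49%.
- The same effect as a normal end score: d = 0.674 + 0.253 = 0.928. Noncentrality = 0.928 × √(15/2) = 2.54 on 28 df. Power = 69%.
- With the Low-arm rate at 25/30/40/50%: binary 82/72/49/29% (Fisher exact 68/56/33/16%); continuous 95/89/69/43%.

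**Step 2. On the QIDS scale, by simulation.** Assumed: baseline mean 16.5 (SD about 3.6-4.2), mean falls of 9 versus 5 points, a linear course and independent residuals. A 50% fall in QIDS at visit 10 stands in for yes/no response. Power (%), 2,000 trials per setting:

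| SD of fall, residual SD | Yes/no | Baseline-adjusted last score | Slopes over ten scores |
|---|---|---|---|
| 3, 2 | 54 | 75 | 84 |
| 4, 2 | 42 | 58 | 66 |
| 4, 3 | 33 | 47 | 56 |
| 3, 3 | 41 | 59 | 69 |
| 5, 2 | 33 | 45 | 51 |

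A repeat with 4,000 trials gave 54/74/84, 41/58/66, 35/49/57, 41/59/71 and 31/46/50. Over both sets, moving from yes/no to the last score gains 12-21 points; moving from the last score to the series gains 4-12. In the first set the SE of the arm difference is 1.30-1.95 points for slopes against 1.46-2.08 for the last score, about 6-11% smaller.

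**Step 3. How the second gain depends on correlation.** Generalised least squares on ten scores, with the arm difference growing linearly from zero and d = 0.928 at the last score. SEs are in SD units; power uses noncentrality 0.928/SE on 28 df.

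| Assumed correlation | SE, series | SE, adjusted last score | Ratio | Power, series v last |
|---|---|---|---|---|
| Compound symmetry 0.5 | 0.231 | 0.316 | 0.73 | 97% v 81% |
| Random slopes (first-last correlation 0.4) | 0.277 | 0.313 | 0.88 | 90% v 82% |
| Random slopes (first-last correlation 0.25) | 0.318 | 0.342 | 0.93 | 80% v 74% |
| AR(1) 0.8 | 0.351 | 0.362 | 0.97 | 72% v 69% |
| AR(1) 0.95 | 0.283 | 0.283 | 1.00 | 88% v 88% |

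The added gain runs from 0 to about 16 points.

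**Step 4. When a simple slope does worse.** Repeating step 2 with correlated residuals, for settings (3,2), (4,3) and (5,2):

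- Visit-to-visit correlation 0.5: last score 75/47/45%, slopes 75/46/45%.
- Correlation 0.8: 76/50/46% against 74/44/45%.
- Early-plateau course with correlation 0.5: 73/49/45% against 67/39/43%. With a plateau the slope estimates about 3.5 points where the true difference is 4.0.

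**Step 5. Exclusions.** If 20% are dropped as incomplete (assumed; 12 per arm), the step 1 binary power becomes Φ[(0.35 − 1.96 × 0.2018)/0.1887] = Φ(−0.24), about 40%.

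**The case against.** The best case for the plan is that most of the loss comes from dichotomising, and a continuous end-of-treatment HRSD-24 would recover most of it without any serial data. That stands: in step 2 the larger gain is always the move from yes/no to the last score. It is also true that QIDS-SR is a self-report secondary scale, collected as standard of care and as a safety measure as well, so the scores are not simply wasted.

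Three stronger readings are tempting, and the documents do not support them.

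- *QIDS-SR plays no part in Study 1, and the arms are compared on a single yes/no.* Section 7.1 tests response and remission. Section 2.1 includes a QIDS-SR cut-off of 0-5 in Aim 1 remission, which 7.1 omits; the two definitions must be reconciled. A cut-off at one time still does not use the series.
- *The whole gap between yes/no and ten scores (18 to 30 points in the step 2 table) is owed to the repeated measurements.* Only 6-10 of those points are, and only with independent residuals and a linear course. Steps 3 and 4 show that this part can vanish or reverse.
- *Ten on-treatment scores would restore the power of the main test.* Nine are on treatment, the last precedes treatment 10, and a secondary model does not change the power of the Aim 1 test.

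**Conclusion.** The gap is real and worth closing at its low cost. The plan analyses the arms only on two end-of-treatment binary outcomes and leaves the QIDS-SR series and the mid-course HRSD-24 without a randomised comparison.

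Under the assumed 9 versus 5 point falls, keeping the score continuous lifts power from about 31-54% to 45-75%. The series may add between nothing and about 16 points. The correlation between visits decides where in that range it falls, and the documents give no information on it. A simple slope was up to 10 points worse than the last score in the least favourable setting tried. The SDs, mean falls and Low-arm rate are all assumed, so the direction of the dichotomising loss is firmer than its size.

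Keeping partial series is a benefit that does not depend on the precision gain. It assumes that scores are missing at random, which matters because collection stops at withdrawal except for adverse events.

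**What to change.** Add to 7.1 a prespecified secondary efficacy analysis, with participants in their randomised arm and a common pre-treatment mean:

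1. **HRSD-24** at baseline, before treatment 6 and Post Tx, in a longitudinal model with visit as a factor. Three visits need only 3 × 4/2 = 6 covariance parameters. Report the High minus Low difference at Post Tx with its 95% CI.
2. **QIDS-SR** at visits 1-10 in a mixed model, with visit as a factor or a linear trend checked against it. Allow for correlated residuals, for example random intercept and slope with autoregressive errors; an unstructured matrix would need 10 × 11/2 = 55 parameters, too many for 30 participants. Report the visit-10 difference with its 95% CI, noting that it reflects nine treatments.
3. State that Section 7's exclusion of participants with missing information does not apply to these models.
4. State whether scores recorded after a treatment change offered under Section 6.3 are kept or set aside in the main analysis, and give the other as a sensitivity analysis.

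The cost is SAP wording, a little more analysis and some model assumptions. No data, visits or participant burden are added, and the Aim 1 binary test and its power stay as they are.
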